6. INVESTIGATIONAL MEDICINAL PRODUCT

PEG-IFN is a chemically modified alpha interferon formed by the covalent attachment of a 40-kD single branched methoxy polyethylene glycol (PEG) moiety to recombinant IFN alfa-2a. Clinical PK studies have shown that PEG-IFN alfa-2a exhibits sustained absorption and low systemic clearance, enabling the maintenance of therapeutic serum concentrations in adults for at least 1 week after a subcutaneous injection of 180 µg of PEG-IFN.

6.1 DOSE AND SCHEDULE OF INVESTIGATIONAL MEDICINAL PRODUCT AND COMPARATOR

Treated subjects will receive PEG-IFN subcutaneously once weekly for 48 weeks with dosing based on the following BSA categories:

Table 8 Dosing Categories

Dose (µg)	BSA Range (m ²)
45	0.51-0.53
65	0.54-0.74
90	0.75-1.08
135	1.09-1.51
180	>1.51

6.2 DOSE MODIFICATIONS, INTERRUPTIONS, AND DELAYS

The intention of the protocol is that subjects remain on PEG-IFN until the completion of the allocated treatment period. However, it is possible that some subjects will encounter transient or prolonged adverse effects at some juncture during their participation in the trial leading to adjustment of the PEG-IFN dosage. To minimize the effects of these modifications on the eventual evaluation of the safety, tolerability, and efficacy of test drug regimens, the principles in the following sections will be used to adjust the dose of PEG-IFN.

If consistent with subject safety, doses should not be held or eliminated. This recommendation stems from concerns that extended periods of lowered drug concentrations in the blood may lead to a failure of virological and immunological control reducing the chance of HBeAg seroconversion and sustained response at the conclusion of therapy. When the investigator considers it prudent to hold a dose, consideration needs to be given to informing the Sponsor of the missed scheduled dose and the reasons the dose was withheld. Investigators should consider if adjusting the dose, either transiently or permanently, might be appropriate rather than holding a dose.

6.2.1 Stopping Rules

Individual subject treatment with PEG-IFN *must* be stopped in the event of any of the following:

- Severe hypersensitivity reactions (e.g., anaphylaxis, angioedema, bronchoconstriction)
- Severe depression (see also Section 6.2.5.5)
- Absolute neutrophil count $< 0.25 \times 10^9$ cells/L or febrile neutropenia (see also Section 6.2.5.1)
- Platelets $< 25 \times 10^9$ cells/L (see also Section 6.2.5.2)

Discontinuation of individual patient treatment with Pegasys should be considered in the event of any of the following:

- *Evidence of hepatic decompensation (e.g., Child-Pugh Class B or C clinical classification [Appendix 2] or clinical evidence such as ascites or varices) (see also Section 6.2.5.3)*
- *Thyroid abnormalities that cannot be effectively controlled by medication*
- *Hypoglycemia, hyperglycemia, or diabetes mellitus that cannot be effectively controlled by medication*
- *New or worsening visual disorders such as field deficits, decrease or loss of vision*
- *Persistent or unexplained pulmonary infiltrates or pulmonary function impairment*
- *Worsening of psoriatic lesion*
- *Development of autoimmunity, including autoimmune hepatitis*
- *Pregnancy (see also Section 7.2.4)*

In the event of discontinuation from treatment, subjects will be encouraged to remain in the 5-year follow-up period (see Section 4.6.1).

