- History of thyroid disease poorly controlled on prescribed medications or clinically relevant abnormal thyroid function tests (thyroid-stimulating hormone [TSH], free triiodothyronine [FT3], free thyroxine [FT4], thyroid peroxidase [TPO] antibodies, and/or thyroxine-binding globulin [TBG]) at screening
- Poorly controlled diabetes
- History of solid organ or bone marrow transplantation
- Evidence of an active or suspected cancer or a history of malignancy in which the risk of recurrence was/is $> 20\%$ within 2 years
- History of having received any systemic anti-neoplastic (including radiation) or immunomodulatory treatment (including systemic corticosteroids) ≤ 6 months prior to the study baseline visit or the expectation that such treatment will be needed at any time during the study (Exception: Topical corticosteroids, corticosteroids prescribed as physiological replacement therapies, or short courses $[\leq 7 \text{ days}]$ of systemic corticosteroids)
- Coagulopathy (international normalized ratio > 1.5), hemoglobinopathy, hemophilia, or history of severe illness or other blood disorders that would make subject unsuitable for the study
- History of seizure disorder requiring treatment with anticonvulsant medication (excluding febrile seizures)
- History or other evidence of severe retinopathy (all subjects to have ophthalmological examination within 6 months prior to baseline)
- History or other evidence of severe illness or any other conditions that would make the subject, in the opinion of the investigator, unsuitable for the study
- Active substance abuse within the last 6 months before the study

- Sexually active females of childbearing potential and sexually active males who are not willing to utilize reliable contraception during the treatment/principal observation period and during the initial 24-week follow-up period
- Females of childbearing potential who have a positive urine or serum pregnancy test result within 24 hours of baseline, or who are breast-feeding

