4.6 CRITERIA FOR PREMATURE WITHDRAWAL

4.6.1 Withdrawal of Subjects from Study Treatment

Subjects have the right to withdraw from study treatment at any time for any reason. Specific rules for stopping study treatment also apply (see Section 6.2.1).

In the case that the subject decides to prematurely discontinue study treatment ("refuses treatment"), all efforts will be made to complete and report the observations prior to withdrawal as thoroughly as possible preferably by returning to site to complete assessments as per the Week 48/Switch Week 48 visit (see Table 2 and Table 4) and the Treatment Completion eCRF. The subject should then enter the post-*end of* treatment follow-up period.

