4.6.2 Withdrawal of Subjects from the Study

Subjects have the right to withdraw from the study at any time for any reason.

In the case that the subject decides not to enter the follow-up period or prematurely discontinues from the follow-up period, he/she should be asked if he/she can still be contacted for further information. The outcome of that discussion should be

documented in the medical records. If the subject is lost to follow-up, the investigator should contact the subject or a responsible relative by telephone followed by registered mail or through a personal visit to establish as completely as possible the reason for the withdrawal. In all cases, the Study Completion eCRF must be completed.

If possible, a complete final evaluation at the time of the subject's withdrawal from the study should be made with an explanation of why the subject is withdrawing from the study. For subjects withdrawing prior to Week 48, the assessments as per the Week 48 visit should be completed. For subjects withdrawing post-Week 48 but prior to follow-up Week 24, the assessments as per the follow-up Week 24 visit should be completed. For subjects withdrawing after follow-up Week 24, the assessments as per the follow-up Year 5 visit should be completed.

When applicable, subjects should be informed of circumstances under which their participation may be terminated by the investigator without the subject's consent/assent. The investigator may withdraw subjects from the study in the event of intercurrent illness, AEs, lack of compliance with the study and/or study procedures (e.g., dosing instructions, study visits) or any reason where it is felt by the investigator that further follow-up of the subject is impossible or it is in the best interest of the subject to be terminated from the study. Any administrative or other reasons for withdrawal must be documented and explained to the subject.

If the reason for removal of a subject from the study is an AE, the principal specific event will be recorded on the eCRF. The subject should be followed until the AE has resolved, if possible.

An excessive rate of withdrawals can render the study non-interpretable; therefore, unnecessary withdrawal of subjects should be avoided. Should a subject decide to withdraw, all efforts will be made to complete and report the observations prior to withdrawal as thoroughly as possible.

See Section [7.2.4](#) for withdrawal due to pregnancy.

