7.2.4 Pregnancy

A female subject must be instructed to stop taking the study medication and immediately inform the investigator if she becomes pregnant during the study. The investigator should report all pregnancies within 24 hours to the Sponsor, using the Pregnancy Report eCRF. The investigator should counsel the subject, and discuss the risks of continuing with the pregnancy and the possible effects on the fetus. Monitoring of the subject should continue until conclusion of the pregnancy. Pregnancies occurring up to 90 days after the completion of the study medication must also be reported to the investigator. Subjects that become pregnant during the treatment period will be withdrawn from the treatment period and continue into the follow-up period.

Pregnancy occurring in the partner of a male subject participating in the study should be reported to the investigator and the Sponsor. The partner should be counseled, the risks

of continuing the pregnancy discussed, as well as the possible effects on the fetus. Monitoring of the subject should continue until conclusion of the pregnancy.

NOTE: The investigator should fill out a Pregnancy Report eCRF only if the pregnant partner has signed a Pregnant Partner Data Release Form.

In the event that the EDC system is unavailable, a Pregnancy Report worksheet and Pregnancy Fax Coversheet should be completed and faxed to Roche Safety or its designee within 1 working day after learning of the pregnancy.

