pregnancy occurs in a subject or partner of a subject during the PEG-IFN treatment period or up to 3 months after PEG-IFN treatment, the cases should be handled as described in Section 7.2.4.

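### Pregnancy is a discretionary reason to stop PEG-IFN in Protocol 6.2.1 and the synopsis, but a mandatory one in Section 7.2.4

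*Protocol*

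**What the plan says.** Protocol 6.2.1 (Stopping Rules) opens with a mandatory list: severe hypersensitivity, severe depression, very low neutrophils or febrile neutropenia, and very low platelets. Pregnancy is not in it. A second list follows, introduced by "Discontinuation of individual patient treatment with Pegasys should be considered in the event of any of the following", and its last item is "Pregnancy (see also Section 7.2.4)". The stopping-rules entry of the protocol synopsis has the same two lists with pregnancy in the same place, but its pregnancy bullet carries no cross-reference.

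Protocol 7.2.4 (Pregnancy) is unconditional, in two statements. The first is "A female subject must be instructed to stop taking the study medication" if she becomes pregnant during the study. The second is "Subjects that become pregnant during the treatment period will be withdrawn from the treatment period and continue into the follow-up period".

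Two other sections route pregnancy to 7.2.4. Section 4.6.2 refers the reader there "for withdrawal due to pregnancy". Section 7.3 says of pregnancies during PEG-IFN treatment or up to 3 months afterwards that "the cases should be handled as described in Section 7.2.4".

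**The concern.** A stopping rule should give one answer to one event. Here an investigator who reads 6.2.1 or the synopsis is told to weigh stopping, and one who reads 7.2.4 is told to stop. Section 6.2 adds some pressure in the wrong direction, because its general principle is to avoid holding or omitting doses where safety allows, and a discretionary item is read against that default.

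What is at stake is exposure of a pregnant minor to interferon. The situation is foreseeable: enrolment runs to just under 18 years, and the protocol schedules pregnancy tests during treatment. Section 7.3 reports an increased incidence of spontaneous abortion in monkeys given high doses of interferon and states that no adequate controlled studies of any interferon exist in pregnant females.

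**Working it through.** No arithmetic applies. The check sets the current texts side by side and asks which actions each allows.

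| Place | Status of stopping for pregnancy |
|---|---|
| Protocol 6.2.1 | Discretionary, with a cross-reference to 7.2.4 |
| Protocol synopsis, stopping rules | Discretionary, no cross-reference |
| Protocol 7.2.4, instruction to the subject | Mandatory |
| Protocol 7.2.4, withdrawal from the treatment period | Mandatory |
| Protocol 4.6.2 | Refers to 7.2.4 |
| Protocol 7.3 | Refers to 7.2.4 |

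**Step 1: compare the two possible actions after a pregnancy on treatment.**
- Stop PEG-IFN: 6.2.1 is satisfied, since stopping was considered and chosen. 7.2.4 is satisfied.
- Consider stopping, then continue: 6.2.1 is satisfied. 7.2.4 is breached.

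The sections therefore differ on one action only. Section 6.2.1 permits continued dosing and 7.2.4 forbids it.

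**Step 2: does the cross-reference reconcile them?** It takes the reader to the stricter rule, but it does not say that rule prevails. In the same section, the same form of cross-reference follows the neutrophil and platelet items, where the detail sections supplement the stopping rule and do not override it. The form alone does not signal precedence.

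**Step 3: which rule should give way?** Three places point to 7.2.4: the bullet in 6.2.1 itself, Section 4.6.2 and Section 7.3. None sends a reader from 7.2.4 back to a discretionary rule. The entry criteria lean the same way: Section 4.3 excludes "Females of childbearing potential who have a positive urine or serum pregnancy test result within 24 hours of baseline", and Section 4.8.2 has the matching bar at switch baseline. Those bars govern starting treatment, so they show consistency of intent but do not themselves settle a stopping rule. The routing in 4.6.2 and 7.3 is the stronger evidence.

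**Step 4: what limits the risk?** Table 2 schedules pregnancy tests for females of childbearing potential at the dispensing visits after baseline (Weeks 4, 8, 12, 18, 24, 30, 36 and 42). Under 7.2.4 the subject herself is told to stop, so stopping need not wait for the investigator's judgement. The same section asks the investigator to report every pregnancy to the sponsor within 24 hours.

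**Step 5: is the analysis affected?** The primary endpoint, the stratified Cochran-Mantel-Haenszel test, the sample size and the definitions of the analysis populations read the same whichever wording stands. Section 7.2.4 also keeps the subject in follow-up.

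**The case against.** The best defence is that the two rules can both be obeyed. Stopping meets both, no site is forced into a breach, and a reader who follows the cross-reference reaches the mandatory rule. This stands as a limit on the risk. It does not remove the conflict, because 6.2.1 still grants a permission that 7.2.4 denies, and the synopsis grants it with no pointer.

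A second defence is that Version E separated the two lists in order to align with prescribing information, so the placement may be deliberate. That source is not available here and the point does not depend on it. If discretion was intended, 7.2.4 is out of step; if it was not, 6.2.1 is. The current text needs one correction either way, and rewording the bullet would leave the split of the lists intact.

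Three stronger readings are tempting, and the documents do not support them:

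- *It is unclear whether continued dosing is a protocol deviation.* It is not unclear. Section 7.2.4 is unconditional, so continued dosing is a deviation.
- *The withdrawal sections lead to different rules.* Section 4.6.1 says "Specific rules for stopping study treatment also apply (see Section 6.2.1)", and the pregnancy bullet in 6.2.1 leads on to 7.2.4. Section 4.6.2 goes to 7.2.4 directly. Both routes end at the same rule, and an extra pointer in 4.6.1 would be a drafting preference.
- *The SAP contains a separate error.* SAP Appendix 1 has the same discretionary list, but it reproduces the protocol synopsis and directs no dosing.

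A reader might also want to bring in hepatic decompensation, which is discretionary in 6.2.1 but calls for permanent discontinuation in 6.2.5.3 when ALT stays above 10 times the upper limit of normal. That is a different topic with its own conditions and forms no part of this point.

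**Conclusion.** Wrong as written; minor, and a matter of safety wording. The contradiction lies in the current protocol text: one operative section (6.2.1) and its synopsis make stopping discretionary, against two mandatory statements in 7.2.4. Section 7.2.4 is the rule to conform to, on the strength of the references to it in 4.6.2 and 7.3.

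The practical risk is limited by the cross-reference, the scheduled tests and the reporting requirement. No frequency can be attached to it, since the documents give no expected number of pregnancies. A reader might infer a threat to the trial's results, but the documents give no basis for that, as nothing in the statistical plan turns on this wording. The verdict assumes that the sponsor means 7.2.4 to govern, as the internal references indicate.

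**What to change.** Make one of two wording changes in Protocol 6.2.1 and in the protocol synopsis:

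- move pregnancy to the mandatory list; or
- leave the bullet where it is and reword it to *Pregnancy (treatment must be stopped; see Section 7.2.4)*.

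The first is cleaner, because a mandatory item under a discretionary heading still invites misreading. Notify sites of the clarification. The copy in SAP Appendix 1 follows the protocol synopsis and needs no decision of its own. Section 4.6.1 and the decompensation rule need no change for this point.

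The cost is a wording-only amendment and a site letter, with no change to design, sample size, data collection or analysis.

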6.2.2 Missing Consecutive Doses

If four or more consecutive doses of PEG-IFN are held or otherwise not administered (i.e., the subject has not received study drug for more than 28 days), the subject will be considered intolerant of the study drug or noncompliant, whichever is more appropriate to the clinical situation. No additional study drug may be administered to such subjects without explicit permission from the Sponsor.

6.2.3 Dose Delay

If a PEG-IFN dose is delayed but eventually administered, the following guidelines should be utilized for the next scheduled dose(s):

- Dose delayed 1 or 2 days: administer on usual dosing day of the week (e.g., the next dose may be administered as usual on Monday).
- Dose delayed 3–5 days: administer subsequent doses every 5th or 6th day until the subject is back to his or her original schedule (e.g., if Monday is the usual dosing day and the dose is delayed until Saturday, the next dose should be administered on Thursday, the following dose on Tuesday, then the dose after that as usual on Monday).
- Dose delayed 6 days: hold the dose for that week then continue on the usual schedule the following week (e.g., if Monday is the usual dosing day but the subject is not ready to be dosed until the following Sunday, the dose is considered to have been held and the next injection should be for the following week's dose on Monday).
- Dose delayed ≥ 7 days: the investigator may reintroduce test drug at any time and, if necessary, dose the subject every 5th or 6th day until the subject resumes weekly dosing on his or her usual scheduled day.

6.2.4 Dose Reduction Levels

Moderate or severe adverse reactions (clinical and/or laboratory) may require dose reduction of PEG-IFN. Decremental adjustments should be uniform across centers and subjects. Toward this end, the following downward adjustments should be utilized:

Starting Dose		One-Level Reduction		Two-Level Reduction		Three-Level Reduction	
(μg)	(mL)	(μg)	(mL)	(μg)	(mL)	(μg)	(mL)
45	0.25	30	0.17	20	0.11	10	0.06
65	0.36	45	0.25	30	0.17	20	0.11
90	0.50	65	0.36	45	0.25	20	0.11
135	0.75	90	0.50	65	0.36	30	0.17
180	1.00	135	0.75	90	0.50	45	0.25

Specific dose adjustment guidance for PEG-IFN is provided in Section 6.2.5 for post-treatment neutropenia, thrombocytopenia, elevated serum ALT, BSA change, and depression.

When practical, abnormal laboratory results should be confirmed as soon as possible following notification of the investigator. If appropriate, downward adjustments in one-level decrements should be considered. It should be kept in mind that, whereas these guidelines should be generally followed to promote consistency across centers, other responses by an investigator may be more appropriate in some circumstances. See Section 7.1.1.1 for definitions of intensity of AEs. For laboratory and vital signs abnormalities, “severe” may be considered as any value requiring intervention, further work-up, or more frequent follow-up.

Once the subject's unit dose has been decreased, the investigator may attempt to increase the dose back to or toward that which was originally assigned only if the following conditions are satisfied:

- The event or circumstance responsible for the dosage adjustment has resolved or improved.
- Subjects who have received more than four consecutive or six total doses at the lower dose level should not generally have their dosage regimen readjusted upward.

6.2.5 Specific Dose Reduction Guidance

6.2.5.1 Dose Adjustments for Low Absolute Neutrophil Counts

Absolute neutrophil count ($\times 10^9$ cells/L)	Response
≥ 0.75	None
0.5–0.749	Immediate one-level adjustment and monitor
0.25–0.499	Delay or hold dose until ≥ 1.0 , then resume dose with two-level adjustment and monitor
< 0.25 or febrile neutropenia	PERMANENTLY DISCONTINUE

6.2.5.2 Dose Adjustments for Low Platelet Counts

Platelets (cells/L)	Response
$< 50 \times 10^9$	Two-level dose reduction
$< 25 \times 10^9$	PERMANENTLY DISCONTINUE

6.2.5.3 Dose Adjustments for Elevated Serum ALT

ALT	Response
< 5 × the ULN	No change.
5–10 × the ULN	Repeat in 1 week. 
 If decreased to < 5 × the ULN, continue dose but monitor to ensure stability. If persistently 5–10 × the ULN on two occasions over 2 weeks, continue dose with one-level adjustment, and monitor ALT until stable or decreasing, then return to full dose If further increased to > 10 × the ULN, follow advice under point (ii) below
> 10 × the ULN	Repeat in 1 week. 
 If decreased to 5–10 × the ULN, continue dose with 1 level adjustment, and monitor ALT until stable or decreasing, then return to full dose. If persistently > 10 × the ULN, hold dose, and carefully monitor ALT and assess for signs of decompensation.^a 
 If there is significant evidence of ALT recovery^b and there are no signs of decompensation, restart dose with one-level reduction. PERMANENTLY DISCONTINUE if there are signs of decompensation.

^a Decompensation is a clinical diagnosis and may be defined as a using a mixture of clinical signs and signs leading to a Child-Pugh score of more than 6 (see [Appendix 2](#)), or the presence of oesophageal varices.

^b Significant decrease in ALT levels may be defined as a progressive decrease in ALT on two serial determinations, with a decline of at least 50% from peak.

6.2.5.4 Dosage Adjustments for BSA Decrease/Increase

Investigators will adjust the dose of PEG-IFN upward or downward to reflect the most current BSA. BSA and dose will be provided by IXRS at Weeks 12, 24, and 36. *Investigators may also assess the patient's BSA (using the Mosteller formula) at other interim timepoints if they are concerned that the BSA and therefore Pegasys dosing category may have changed. It is recommended that an online calculator is utilized for the BSA calculation.*

Mosteller Formula:

$$BSA (m^2) = \sqrt{([Height(cm) \times Weight(kg)] / 3600)}$$

If a subject's BSA falls below < 0.51 m² during treatment, any dose adjustments should be made only after consultation between the investigator and *the Medical Monitor* ([Appendix 3](#)) or *delegate*. The recommended dose will be recorded in the SMD.

